8.2.3.3.2. Holding rules assessed during IDMC evaluations

The Holding rules in [Table 18](#) will be assessed by the IDMC during safety evaluations of unblinded data.

Note that these rules have been written under the assumption that the safety data from all expected subjects will be available. If the data from all subjects are not available (i.e. in case a subject is lost to follow-up), then the holding rules will be assessed on a pro-rata basis.

Further note that the IDMC may recommend that the study be placed on hold for reasons not covered by the holding rules if deemed necessary. Any available safety data may be reviewed as requested by the IDMC to allow for an overall assessment of the benefit/risk ratio of vaccination.

If the study is placed on hold, the investigator must suspend enrolment and study vaccine/product administration. As noted in [Section 8.2.3.3.1](#), the investigator is not permitted to start the administration of the next dose or enrol additional subjects until provided with written documentation of the favourable outcome of the IDMC evaluation, and written authorization to proceed.

Table 18 Holding rules assessed during IDMC evaluations

| Holding Rule | Event | Number of mothers/infants ¹ |
|--------------|--|---|
| 2a | Any Grade 3 solicited administration site event lasting 48h or more in an investigational RSV group, within the 7-days (Day 1-7) post-vaccination period. | ≥ 4 subjects and ≥ 25% across active vaccine groups |
| 2b | Any Grade 3 solicited systemic event lasting 48h or more in an investigational RSV group, within the 7-days (Day 1-7) post-vaccination period. | ≥ 4 subjects and ≥ 25% across active vaccine groups |
| 2c | Any Grade 3 unsolicited AE in an investigational RSV group that cannot be reasonably attributed to a cause other than vaccination, within the 7-days (Day 1-7) post-vaccination period. OR Any Grade 3 abnormality in pre-specified hematological or biochemical laboratory parameters in an investigational RSV group, at Day 8 post-vaccination ² . | ≥ 4 subjects and ≥ 25% across active vaccine groups |

¹ Across active vaccine groups, both conditions need to be achieved together: at least 4 subjects with the corresponding symptoms and at least 25% of subjects with the corresponding symptoms.

² Grading of laboratory parameters will be based on reference ranges as provided in [\[Sheffield, 2013\]](#) and in the SPM for this study.

GSK will inform the investigator of any holding rules in [Table 18](#) (2a-2c) that are met.

CONFIDENTIAL209544 (RSV MAT-004)
Protocol Amendment 3 Final

The below flow of communication must be followed.

- IDMC Chair (or his/her representative) notifies the Clinical Research & Development Lead (CRDL).
- CRDL informs local sponsor contacts / Local Medical Leads (LMLs) and ensures that SBIR is blocked.
- The central sponsor team ensures that all country or region- specific regulatory authorities are informed.
- LMLs inform study sites to place a hold on screening activities and dose administration.
- Informed study sites confirm to their local sponsor contact(s) that action has been taken, providing appropriate documentation to their local GSK sponsor contact.
- The GSK Vaccine Safety Monitoring Board evaluates the case after receipt of the IDMC's recommendations and takes the decision to stop or to restart dose administration.
- Where required per local / regional regulation, the central sponsor team submits a substantial amendment to the local/regional authority requesting authorization to re-start the study and will not re-start the study until approval of the substantial amendment.
- When all required authorizations to re-start the study have been provided, the CRDL / central sponsor team provides written notification to local sponsor contacts; local sponsor contacts then provide written notification to study sites.

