8.2.3.3.3. Overview of IDMC reviews

The IDMC will receive an unblinded report approximately monthly, once enrolment has started. For each report, the IDMC will be provided with available safety data, including but not limited to SAEs, pregnancy outcomes, pregnancy-related and neonatal adverse events of special interest, medically attended RTIs in maternal subjects and RTI/LRTIs in infants. Continuous monthly monitoring throughout the study will allow for ad-hoc data review meetings if deemed necessary by the IDMC.

In addition, there will be 5 planned IDMC data review meetings:

- The first planned meeting will take place once 75 maternal subjects have been dosed;
- Additional meetings will occur to coincide with release of results from each of the analyses described in Section [9.5.1](#).

For each review, the IDMC will be provided with unblinded safety data as described above.

The IDMC will also review all safety data on infant subjects through 1 year of age.

CONFIDENTIAL209544 (RSV MAT-004)
Protocol Amendment 3 Final

As part of ongoing review, the IDMC will monitor the rates of pregnancy-related outcomes and pregnancy-related and neonatal AESIs. Observed rates of outcomes and of AESIs for active vaccine recipients that are **higher** than rates reported in the placebo group or expected in the general population may trigger enhanced scrutiny of the cases by the IDMC. *Examples* based on a 2-fold higher reporting rate in vaccine recipients as compared to the general population are listed in [Table 19](#). For example, with 16 maternal infant pairs followed through delivery, no more than 2 cases of pre-term birth should be expected among the vaccinated group. If that number is 4 or greater, it could be an early indication that vaccination may be harmful and would prompt further scrutiny by the IDMC, including the possibility to hold further vaccination. Depending on the nature and severity of the outcome or AESI, enhanced scrutiny may be triggered even if there is a less than 2-fold increase in reporting rate in vaccine recipients compared to that expected in the general population or seen in the placebo group.

Table 19 Examples of rates for AESIs

| Event of Special Interest | Reported Rate in general population | Rate that could trigger additional safety concern (for the active vaccine groups combined) | | |
|---------------------------------|-------------------------------------|--|---|---|

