8.2.3.4. Risk assessment

[figure not shown]
[Figure 5](#) illustrates the probability of not meeting holding rule 1 and 2 for 16 active vaccine recipients at the first planned IDMC meeting.

CONFIDENTIAL

209544 (RSV MAT-004)
Protocol Amendment 3 Final

Figure 5 Evaluations based on 16 active recipients - Risk assessment curve for one formulation based on the proposed safety holding rules across active groups

Safety holding rule after 16 subjects in active vaccine groups enrollment

Thus, with 16 active vaccine recipients across study groups:

- Each holding rule 1a-1c has a more than 90% chance of not being met for vaccination with a true incidence rate below 1% and has a more than 80% chance of being met for vaccination with a true incidence rate above 10%.
- Each holding rule 2a-2c has a more than 90% chance of not being met for vaccination with a true incidence rate below 10% and a more than 80% chance of being met for vaccination with a true incidence rate above 35%.

The risk of ERD related to boosting pre-existing maternal antibody and transfer of vaccine-induced neutralizing antibodies from mother to infant, is considered negligible. However, as data evaluating this risk are expected before the vaccination of larger numbers of pregnant women, surveillance and evaluation of all RTIs in infants and medically attended-RTIs in mothers (Section 8.4) has been implemented.

To assess the ability of the study to demonstrate with 90% power that the progression rate from RSV infection to severe disease or hospitalization is lower than the 80% rate seen in the historical formalin-inactivated vaccine, the accrual of at least 5 cases of RSV infection among infants will be needed. With a one-sided 5% type one error rate and assumption of a 10% rate of infection progressing to severe disease or hospitalization, 5 infections can provide at least 90% statistical power to demonstrate the progression rate from RSV infection to severe disease or hospitalization is less than 80%.

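### Section 8.2.3.4 misstates the operating characteristics of the holding rules: wrong number of recipients, a rule 1 figure that fails, and an unstated common-rate assumption for rule 2

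*Protocol*

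**What the plan says.** Table 18 (Protocol 8.2.3.3.2) defines the rule 2 events by group, for example "Any Grade 3 solicited systemic event lasting 48h or more in an investigational RSV group". The count column sets the trigger at "≥ 4 subjects and ≥ 25% across active vaccine groups", and footnote 1 confirms that both the count and the percentage are taken over the active groups together: "Across active vaccine groups, both conditions need to be achieved together: at least 4 subjects with the corresponding symptoms and at least 25" per cent.

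Section 8.2.3.4 gives the resulting probabilities "for 16 active vaccine recipients at the first planned IDMC meeting". For rule 1 it says: "Each holding rule 1a-1c has a more than 90% chance of not being met for vaccination with a true incidence rate below 1" per cent. For rules 2a-2c it claims more than 90% not met below a 10% rate, and "a more than 80% chance of being met for vaccination with a true incidence rate above 35" per cent. The Figure 5 caption reads "Risk assessment curve for one formulation based on the proposed safety holding rules across active groups".

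Section 8.2.3.3.3 fixes the timing differently: "The first planned meeting will take place once 75 maternal subjects have been dosed". Allocation is 1:1:1 (6.3.2).

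**The concern.** Section 8.2.3.4 is where the protocol tells investigators, ethics committees and the IDMC how sensitive the holding rules are, in the first pregnant women to receive this vaccine. Three things there do not fit.

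- The sample size disagrees with the meeting it is attached to.
- The rule 1 statement looks too favourable for a rule that fires on a single event.
- The rule 2 probabilities come from a pooled count, while the caption invites the reader to apply them to one formulation.

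A reader who takes the last at face value would think that a 35% rate of the trigger event in one dose is caught at least 80% of the time. If the other dose is well tolerated, that is far from true, and the shortfall is larger at 50 recipients than at 16.

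**Working it through.** **Inputs.** Trigger: at least 4 subjects and at least 25%, active groups combined (Table 18). Stated size: 16 active recipients (8.2.3.4). First planned IDMC meeting: 75 dosed (8.2.3.3.3). Allocation 1:1:1 (6.3.2). Rule 1: one event or more (Table 17).

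**Size at the first planned meeting.** 75 × 2/3 = 50 active, about 25 per dose; slightly fewer will have complete Day 8 data. The 16 matches the mother-infant pairs followed to delivery in the preterm-birth example of 8.2.3.3.3. It does not match the Day 1-7 and Day 8 data that rules 2a-2c use.

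**Rule 2, common rate p.** Threshold r = max(4, 25% of n, rounded up); P(met) = P(X ≥ r), X ~ Binomial(n, p).

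- n = 16, r = 4: not met at 10% = 93.2%; met at 35% = 86.6%. The protocol's two figures reproduce.
- n = 50, r = 13: not met at 10% = 99.9%; met at 35% = 93.4%.

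**Rule 1.** P(not met) = (1 − p)^n.

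- p = 1%: 0.99^16 = 85.1%; 0.99^50 = 60.5%. Neither reaches 90%.
- The largest p that gives 90% is 1 − 0.9^(1/n): 0.66% for n = 16, 0.21% for n = 50.
- p = 10%: met with probability 1 − 0.9^16 = 81.5%, as the protocol claims (more than 80%), and 1 − 0.9^50 = 99.5%.

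**Rule 2, unequal rates.** The pooled count is the sum of two independent binomials. With 35% in one dose:

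| Rate in other dose | 8+8 (4 of 16) | 25+25 (13 of 50) |
|---|---|---|
| 0% | 29% | 6% |
| 5% | 40% | 17% |
| 10% | 51% | 32% |
| 15% | 60% | 49% |
| 26% | 77% | 80% |
| 30% | 82% | 87% |

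**What a by-dose check would cost.** Apply the same test within each dose. The thresholds are 5 of 20, 6 of 24 and 7 of 25. At 35% in that dose it is met 88%, 90% and 83% of the time. At a common 10% rate, the chance that either dose triggers one rule is 8.4%, 5.5% and 1.9%. For any of three rules, taken as independent, it is 1 − (1 − that chance)^3:

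| Per dose | By-dose check | Pooled rule |
|---|---|---|
| 20 | 23% | 1.5% |
| 24 | 15.5% | 0.7% |
| 25 | 5.6% | 0.3% |

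These are per look; repeated looks add to them.

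**The case against.** Pooling is an open choice. It appears in the count column, in footnote 1, and in the words next to the figures in 8.2.3.4. The event column's reference to an investigational group can simply mean that placebo events do not count, so Table 18 does not contradict itself. The caption's mention of one formulation might be meant as shorthand for a single rate; the curve itself is not shown.

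Three stronger readings are tempting, and the documents do not support them.

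- *The rule 2 assurance holds only if both doses share one rate.* The pooled rule mainly follows the average rate. Rates of 30% and 40% at 8+8 give 86.8%, and 35% with 26% at 25+25 gives 80%. It fails when one dose is high and the other low.
- *The 16-versus-50 mismatch makes the rule 2 figures false.* Under a common rate both statements are correct at 16 and stronger at 50.
- *The protocol needs an automatic by-dose hold.* The IDMC is unblinded, gets reports about monthly, may recommend a hold outside the rules (8.2.3.3.2) and may act on selected groups (8.2.3.2). Rules 1a-1d fire on single events. Both doses were chosen after safety review in non-pregnant women (4.3). The IDMC charter and its separate SAP are not shown and may already provide by-dose review. An automatic trigger would raise false holds materially, and each hold stops screening and dosing and may need an approved substantial amendment, in a trial with a dosing window of 28 0/7 to 33 6/7 weeks.

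What remains after these objections is the text of 8.2.3.4: the size, the rule 1 figure and the missing condition on rule 2.

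**Conclusion.** Section 8.2.3.4 is wrong as written on two points and incomplete on a third. The 16 recipients contradict the 75-dosed meeting, which implies about 50 active. The rule 1a-1c claim fails at the stated 16 (85.1% at a 1% rate) and more clearly at 50 (60.5%). The rule 2 figures are right for pooled groups at a common rate, but that condition is not given and the caption points away from it.

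The pooled design itself is a defensible choice. Its weakness against a one-dose signal should be disclosed rather than designed out. The results rest on 1:1:1 allocation, independent subjects, complete data for the recipients counted and, for the three-rule figures, independence between rules. The one-dose scenarios are illustrations; the documents give no expected event rates by dose.

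**What to change.** Restate 8.2.3.4 as follows.

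1. Base it on about 50 active recipients at the first planned meeting. Rule 2: 99.9% not met at 10%, 93.4% met at 35%. Rule 1: 61% not met at 1%, 99.5% met at 10%.
2. Replace the rule 1 threshold. A 90% chance of not being met holds only below about 0.21% at 50 (0.66% if 16 is kept as an illustration).
3. State that the rule 2 figures assume the same rate in both doses, and align the Figure 5 caption.
4. Add the single-dose figures from the table above, so that the IDMC knows the pooled trigger is weak when only one dose is affected.

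Optionally, offer the same count-and-percentage test within each dose as a prompt for IDMC review, from 20 evaluable recipients per dose, without an automatic hold.

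The cost is amended text and a redrawn Figure 5, with ethics approval where the amendment requires it; it can go with the next amendment. No extra data or visits are needed. The optional prompt adds some IDMC review time, at the false-alarm rates shown above.

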8.2.3.3.3. Overview of IDMC reviews

The IDMC will receive an unblinded report approximately monthly, once enrolment has started. For each report, the IDMC will be provided with available safety data, including but not limited to SAEs, pregnancy outcomes, pregnancy-related and neonatal adverse events of special interest, medically attended RTIs in maternal subjects and RTI/LRTIs in infants. Continuous monthly monitoring throughout the study will allow for ad-hoc data review meetings if deemed necessary by the IDMC.

In addition, there will be 5 planned IDMC data review meetings:

- The first planned meeting will take place once 75 maternal subjects have been dosed;
- Additional meetings will occur to coincide with release of results from each of the analyses described in Section [9.5.1](#).

For each review, the IDMC will be provided with unblinded safety data as described above.

The IDMC will also review all safety data on infant subjects through 1 year of age.

CONFIDENTIAL209544 (RSV MAT-004)
Protocol Amendment 3 Final

As part of ongoing review, the IDMC will monitor the rates of pregnancy-related outcomes and pregnancy-related and neonatal AESIs. Observed rates of outcomes and of AESIs for active vaccine recipients that are **higher** than rates reported in the placebo group or expected in the general population may trigger enhanced scrutiny of the cases by the IDMC. *Examples* based on a 2-fold higher reporting rate in vaccine recipients as compared to the general population are listed in [Table 19](#). For example, with 16 maternal infant pairs followed through delivery, no more than 2 cases of pre-term birth should be expected among the vaccinated group. If that number is 4 or greater, it could be an early indication that vaccination may be harmful and would prompt further scrutiny by the IDMC, including the possibility to hold further vaccination. Depending on the nature and severity of the outcome or AESI, enhanced scrutiny may be triggered even if there is a less than 2-fold increase in reporting rate in vaccine recipients compared to that expected in the general population or seen in the placebo group.

Table 19 Examples of rates for AESIs

| Event of Special Interest | Reported Rate in general population | Rate that could trigger additional safety concern (for the active vaccine groups combined) | | |
|---------------------------------|-------------------------------------|--|---|---|
| | | % of subjects | Number of subjects in vaccinated groups at IDMC meeting 1 | Number of subjects in vaccinated groups at IDMC meeting 2 |
| Gestational hypertension | 8% | 16% | 3 | 16 |
| Gestational diabetes | 6-7% | 14% | 3 | 14 |
| Small for gestational age | 10% | 20% | 4 | 20 |
| Non-reassuring fetal status | 15% | 30% | 5 | 30 |
| Preterm Birth | 12% | 24% | 4 | 24 |
| Low birth weight | 8% | 16% | 3 | 16 |
| Respiratory distress/asphyxia | 10% | 20% | 4 | 20 |
| Antenatal bleeding | 4-5% | 10% | 2 | 10 |
| Intrauterine growth restriction | 3-7% | 14% | 3 | 14 |

Enhanced scrutiny of the cases by the IDMC can be triggered at any point during the study depending on the observed rate of an AESI or any other safety concern.

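### The numbers of women attached to IDMC meetings 1 and 2 do not match the stated meeting triggers, and the rule 1 probability is wrong at its own n of 16

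*Protocol*

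**What the plan says.** Protocol Section 8.2.3.3.3 plans five IDMC meetings. For the first it says "The first planned meeting will take place once 75 maternal subjects have been dosed". For the rest it says "Additional meetings will occur to coincide with release of results from each of the analyses described in Section" 9.5.1, so meeting 2 goes with the first analysis. Section 9.5.1.1 triggers that analysis when about 75 women have completed Day 31 and about 24 mother-infant pairs have completed delivery.

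Table 19 in the same section gives, for nine events, a background rate, a trigger percentage of twice that rate (twice its upper end where a range is given), and two columns of counts labelled by meeting. The second is headed "Number of subjects in vaccinated groups at IDMC meeting 2". Two of its rows read "Preterm Birth | 12% | 24% | 4 | 24" and "Gestational hypertension | 8% | 16% | 3 | 16".

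Section 8.2.3.4 introduces Figure 5 as the chance of not meeting the holding rules "for 16 active vaccine recipients at the first planned IDMC meeting", and the figure text reads "Safety holding rule after 16 subjects in active vaccine groups enrollment". The bullets below the figure state, for 16 active recipients, "Each holding rule 1a-1c has a more than 90% chance of not being met for vaccination with a true incidence rate below 1" per cent.

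**The concern.** Two kinds of stated figure appear to be wrong. First, the sizes used to illustrate the safety reviews do not follow from the triggers that define those reviews. A reader who used Table 19 by meeting number could hold counts worked for about 100 active women against a meeting triggered at half that number, or at about one sixth of it for birth outcomes. The error is in the direction of later scrutiny.

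Second, one of the four operating characteristics given for the holding rules looks too favourable. A rule 1 hold suspends enrolment and dosing and brings in the regulators, so its chance of occurring at a low event rate should be stated correctly. This is the first exposure of pregnant women to the vaccine.

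**Working it through.** **Inputs.** Allocation is 1:1:1 (Section 6.3.2), so two thirds of women are active. Rules 1a to 1d are met by one event or more (Table 17). Rules 2a to 2c need at least 4 subjects and at least 25% of active recipients (Table 18). The meeting triggers and Table 19 percentages are those described above.

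**Step 1: active women at each trigger.**

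| Meeting | Stated trigger | Active women (× 2/3) | Size used in the text |
|---|---|---|---|
| 1 | 75 dosed | 50 | 16 enrolled (Figure 5) |
| 2 (first analysis) | 75 at Day 31; 24 delivered | 50; 16 | 97 to 100 (Table 19, Step 2) |

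The figure text counts women enrolled, so its 16 cannot be read as a number delivered. Sixteen does equal 24 × 2/3, but that is the delivery count at the first analysis, which is meeting 2. One hundred equals 150 × 2/3, but 150 is the trigger of the third analysis (Section 9.5.1.3), which is meeting 4.

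**Step 2: the n behind each Table 19 column.** I rounded trigger percentage × n up to the next whole number and looked for the n that gives all nine counts.

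- Meeting 1 column (3, 3, 4, 5, 4, 3, 4, 2, 3): only n = 16. For example, 0.24 × 16 = 3.84, giving 4. Rounding to nearest gives only n = 18.
- Meeting 2 column (16, 14, 20, 30, 24, 16, 20, 10, 14): only n = 97 to 100. Rounding to nearest gives 99 to 101.

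Ninety-seven to 100 active women means about 146 to 150 women in all three groups.

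**Step 3: size of the meeting 2 mismatch.**

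- *Birth outcomes.* The printed counts for preterm birth (24), small for gestational age (20) and respiratory distress (20) all exceed the 16 active deliveries at the trigger. At n = 16 the table's percentages give 4, 4 and 4. The number delivered by release is not stated. If it were 24, 32 or 50 active (assumed), 24 preterm births would be 100%, 75% or 48%, against the table's 24%.
- *Events not limited to delivered women.* At 50 active, the percentages give 8 for gestational hypertension, 7 for gestational diabetes, 5 for antenatal bleeding and 7 for growth restriction. The printed counts are 16, 14, 10 and 14. Relative to the upper background rate, the hypertension count is 16/50 ÷ 0.08 = 4.0-fold, and the other three rows give the same ratio. It is 2.7-fold at an assumed 75 active, and the intended 2-fold at 100.

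No mismatch is claimed for the birth-outcome rows of the meeting 1 column. The protocol does not say how many women will have delivered when 75 have been dosed.

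**Step 4: operating characteristics at n = 16.** For rule 1, P(not met) = (1 − p)^16. For rule 2 the threshold is 4 of 16, evaluated by the exact binomial.

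| Statement in Section 8.2.3.4 | Stated | Computed |
|---|---|---|
| Rule 1 met at 10% | over 80% | 1 − 0.90^16 = 81.5% |
| Rule 2 not met at 10% | over 90% | 93.2% |
| Rule 2 met at 35% | over 80% | 86.6% |
| Rule 1 not met at 1% | over 90% | 0.99^16 = 85.1% |

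Three of the four reproduce, which supports the method and isolates the fourth. The chance of a rule 1 hold at a 1% rate is 14.9%, not under 10%. Solving (1 − p)^16 = 0.90 gives p = 1 − 0.90^(1/16) = 0.656%, so the statement fails for true rates from there up to 1%.

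No other n makes the whole rule 1 sentence true. Over 90% not met at 1% needs n ≤ 10, because ln 0.90 / ln 0.99 = 10.5. Over 80% met at 10% needs n ≥ 16, because ln 0.20 / ln 0.90 = 15.3.

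**Step 5: what the curve would show at the actual meeting 1 trigger.** With 50 active recipients, rule 1 has a 60.5% chance of not being met at 1% and a 99.5% chance of being met at 10%. Rule 2 then needs 13 subjects (25% of 50, rounded up). It has a 99.9% chance of not being met at 10% and a 93.4% chance of being met at 35%.

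**The case against.** The strongest reply concerns Table 19. Later meetings are tied to the release of results, not to the analysis trigger, and the IDMC receives whatever safety data are then available. Dosing is unrestricted after the first 30 women, so more than 50 active women could be under follow-up by release. About 100 is therefore not excluded for the antenatal rows. The table is also labelled as examples, its percentage column is correct at any n, and the worked example beside it states its denominator. An unblinded committee that receives roughly monthly reports, and may look harder at any time, would not hold 24 preterm births against 16 deliveries. The charter and the separate IDMC analysis plan are not shown. Rule 1 is applied continuously by investigators whatever the number enrolled, so the probability sentence describes a curve and sets no threshold.

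Most of this stands as a limit on consequence. It is fair that the 4.0-fold figure uses the trigger as the denominator and that the larger denominators are assumptions. For the antenatal rows, the firm statement is that nothing in the protocol leads to about 100 active women at meeting 2. The reply does not reach the other two points. Sixteen enrolled recipients and about 50 cannot both describe the first meeting, and 85.1% is not above 90%.

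**Conclusion.** The point holds, as a minor one. The n of 16 given for the first planned meeting contradicts the trigger of 75 dosed women, which is about 50 active. The meeting 2 column of Table 19 was worked for 97 to 100 active women, a size that no stated meeting 2 trigger produces. The clearest inconsistency is in the birth-outcome rows, where three printed counts exceed the number of active deliveries at the trigger. The rule 1 statement is false for true rates between 0.656% and 1%, and at 1% it understates the chance of a hold (14.9% against an implied figure below 10%).

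This rests on exact 1:1:1 allocation at each trigger, on the Table 19 counts having been rounded up (rounding to nearest changes the implied n only slightly), and on independent events with a common rate. No holding rule, analysis or study procedure depends on the wrong figures.

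**What to change.** Three edits to the protocol, repeated in the IDMC charter if it carries the same text:

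1. **Table 19.** Relabel the two count columns as n = 16 and n = 100. Alternatively, drop the counts and keep the percentage with the denominator to use: active women delivered for birth outcomes, active women followed for antenatal events.
2. **Section 8.2.3.4, introduction to Figure 5.** Delete the reference to the first planned IDMC meeting, so that the figure simply describes 16 active recipients.
3. **Section 8.2.3.4, rule 1 bullet.** State about an 85% chance of not being met at a true incidence of 1%, or keep the 90% figure and lower the rate to below about 0.65%.

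The cost is two column labels, one deleted phrase and one corrected figure. Conduct and the holding rules stay as they are.

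### Table 19 labels its example 2-fold AESI counts by IDMC meeting, but the counts belong to 16 and about 100 active recipients, not to the numbers the schedule gives at those meetings

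*Protocol*

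**What the plan says.** Section 8.2.3.3.3 plans five IDMC data review meetings. For the first, "The first planned meeting will take place once 75 maternal subjects have been dosed"; for the rest, "Additional meetings will occur to coincide with release of results from each of the analyses" in Section 9.5.1. One meeting plus four analyses makes five, so meeting 2 goes with the first analysis. Section 9.5.1.1 triggers that analysis at about 75 women past Day 31 and about 24 deliveries. Section 6.3.2 allocates 1:1:1 to two active groups and placebo.

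Table 19 lists background rates, doubled rates, and counts for the combined active groups in two columns, one for meeting 1 and one headed "Number of subjects in vaccinated groups at IDMC meeting 2". Typical rows are "Preterm Birth | 12% | 24% | 4 | 24", "Small for gestational age | 10% | 20% | 4 | 20" and "Gestational hypertension | 8% | 16% | 3 | 16". The text above the table gives a worked example: "with 16 maternal infant pairs followed through delivery, no more than 2 cases of pre-term birth should be expected among the vaccinated group". Four or more would prompt further scrutiny and possibly a hold on vaccination.

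Section 8.2.3.4 then describes the chance of not meeting the holding rules "for 16 active vaccine recipients at the first planned IDMC meeting".

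**The concern.** The protocol gives two incompatible sizes for meeting 1: 75 dosed (about 50 active) and 16 active. For meeting 2 the table prints a preterm count of 24, while the worked example treats 4 among 16 pairs as a possible early sign of harm, and 16 active pairs is what the meeting 2 trigger delivers.

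This is the vaccine's first use in pregnant women, and Table 19 holds the protocol's rate-based AESI benchmarks. Counts set beside the wrong meeting can mislead in both directions. At meeting 1 they are low for 50 recipients. At meeting 2 they are far too high for 16 births.

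**Working it through.** **Inputs.** Table 19 percentages, in table order: 16, 14, 20, 30, 24, 16, 20, 10, 14 (hypertension, diabetes, small for gestational age, non-reassuring fetal status, preterm birth, low birth weight, respiratory distress, antenatal bleeding, growth restriction). Background rates are half of these, taking the upper end where a range is given. Active share is 2/3.

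**Step 1: reproduce the printed counts.** Count = percentage × n, rounded up.
- n = 16 gives 3, 3, 4, 5, 4, 3, 4, 2, 3, which is the meeting 1 column. No other n from 1 to 200 fits all nine rows.
- n = 100 gives 16, 14, 20, 30, 24, 16, 20, 10, 14, which is the meeting 2 column. Any n from 97 to 100 fits.
- Rounding to nearest gives 18 and 99–101. Rounding down gives no fit and 100–103. No convention gives 50 for the first column or 16 for the second.

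**Step 2: what the schedule gives.**
- Meeting 1: 75 × 2/3 = 50 active dosed.
- Meeting 2, at the first-analysis trigger: 24 × 2/3 = 16 active births, possibly more by the time results are released.

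**Step 3: meeting 2 counts against 16 active births.** Preterm 24/16, small for gestational age 20/16 and respiratory distress 20/16 all exceed 1. Low birth weight, 16/16, would need every infant.

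**Step 4: meeting 2 counts if many more have delivered.** Assume 50 active births (an assumption; the protocol does not give the figure). Each printed count is then 4 times the listed upper background rate, for example 24/50 = 48% against 12%. The binomial chance that a true doubling reaches the printed count is:

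| Event | Count | P at n=50 |
|---|---|---|
| Hypertension, low birth weight | 16 | 0.0038 |
| Diabetes, growth restriction | 14 | 0.0073 |
| Small for gestational age, respiratory distress | 20 | 0.0009 |
| Non-reassuring fetal status | 30 | 0.00001 |
| Preterm birth | 24 | 0.0002 |
| Antenatal bleeding | 10 | 0.0245 |

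At n = 100, the size the counts fit, the same chance is 54–55% in every row.

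**Step 5: meeting 1 counts against 50 active dosed.** For hypertension, diabetes, growth restriction and antenatal bleeding, counts of 2–3 are 4–6% of 50, or 0.75–0.86 times the listed upper rate. With no vaccine effect they are reached 69–77% of the time if the full background rate has accrued, 26–36% if half has, and 6–13% if a quarter has. The protocol does not state follow-up at that date.

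**Step 6: Section 8.2.3.4.** Rule 1 needs one event; rule 2 needs at least 4 subjects and at least 25%.
- Rule 1 not met at a 1% rate: 0.99^16 = 85.1%; 0.99^50 = 60.5%. The protocol states more than 90% for rates below 1%.
- Rule 1 met at 10%, n = 16: 1 − 0.9^16 = 81.5%, which agrees with the stated 80%.
- Rule 2 at n = 16 (4 of 16): not met at 10% with probability 93.2%, met at 35% with 86.6%. Both stated figures hold.
- Rule 2 at n = 50: 25% is 12.5, so 13 are needed; not met at 10% with probability 99.9%, met at 35% with 93.4%.

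**The case against.** The strongest reply is that little turns on the labels. The entries are called examples, and no holding rule uses them. The IDMC is unblinded, sees data about monthly, compares rates with placebo and the general population, and may act on less than a doubling or at any time. The percentage column is right, and the worked example beside the table would alert a committee facing 4 preterm births in 16. IDMC procedures also sit in a charter and a separate analysis plan. All of this stands, and it limits the consequence. It does not make the headings agree with the meeting schedule in the same section.

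Stronger readings are tempting, and the protocol does not support them:
- *Table 19 is the only numerical AESI threshold.* It is not: holding rule 1a in Table 17 acts on a single maternal death, fetal death or unexplained neonatal or infant death.
- *The meeting 2 counts are impossible.* That holds at exactly 16 active births, which is a floor. The trigger is approximate, the meeting follows release of results, and the number dosed by then is not fixed, so the rows for maternal events before delivery may be less far off.
- *Meeting 1 would raise a false alarm about 70% of the time.* That needs all 50 women to have accrued the full background rate on the day the 75th is dosed, when the last have almost no follow-up and several conditions already present at entry were exclusions. The 6–36% part of the range is the realistic one.

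**Conclusion.** The mislabelling is confirmed, and it is minor. Under rounding up, which also matches the worked example, the first count column fits 16 active recipients and the second 97–100. The schedule gives about 50 active dosed at meeting 1 and about 16 active births at the meeting 2 trigger. Section 8.2.3.4 contradicts the 75-dosed timing directly, and its rule 1 statement is wrong even at its own n of 16.

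The conclusion rests on 1:1:1 allocation and on meeting 2 being the first analysis, both from the protocol. The size at meeting 2 depends on how many have delivered: several counts exceed the births at 16, and at 50 a doubling reaches them at most 2.5% of the time. A reader might infer that the safety monitoring fails or that the IDMC would miss a signal. The protocol does not support that, because the percentages are right and the committee is not bound by the counts.

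**What to change.** Keep every percentage and count in Table 19. Replace the two count headings with denominators and no meeting numbers: *per 16 active recipients followed through delivery* and *per 100 active recipients followed through delivery*. Tagging the second column to the third analysis (meeting 4) would mislabel it again. By the time about 150 pairs have completed Day 181, at least about 100 and up to 200 active women will have delivered, and 24 preterm births in 200 is exactly the 12% background.

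Add one sentence: at each review, apply the percentage column to the active recipients followed through delivery at that date and round up. For 50 this gives 8, 7, 10, 15, 12, 8, 10, 5 and 7 in table order.

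In Section 8.2.3.4, either delete the reference to the first planned IDMC meeting or restate the section, with Figure 5, for 50 active recipients using the rule 2 figures above. Correct the rule 1 statement either way: 85% at n = 16 or 60.5% at n = 50, for a 1% rate.

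The cost is two headings, one sentence and a short correction, carried into the IDMC charter and IDMC analysis plan where they repeat these figures. No new data or outside rates are needed. The counts behave as they already do at their own denominators: with no effect at the listed upper rates, each is reached 7–19% of the time at n = 16 and at most 2.8% at n = 100.
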